## **6.5. Concomitant Therapy**

All medications (including over the counter drugs, vitamins, and antacids) and over the counter emollient(s) taken/used at screening and throughout the study must be recorded. Participants should be instructed to consult with the investigator prior to initiating any new medication (either self-administered non-prescription drugs or prescription therapy prescribed by another physician) while participating in the study. The investigator is expected to examine the acceptability of all concomitant medications, topical preparations, and dietary supplements taken by participants participating in the study.

- Medication entries should be specific to product name (if a combination drug product) and spelled correctly.
- The brand and specific product name for any over the counter emollient(s) should be noted and spelled correctly.

- Information on the dose, unit, frequency, route of administration, start date, discontinuation date, indication, and reason for use will be recorded.
- The use of any concomitant medication must relate to an AE listed on the AE eCRF or the participant's medical history, unless the medication is a supplement or used as preventive care

### **6.5.1. Permitted and Prohibited Treatments and Procedures**

Participants should not apply emollients or other topical treatments on the day of their study visit prior to the procedures to allow adequate assessment of skin dryness.

The use of concomitant medications for other medical conditions (for example, hypertension, diabetes, acute infections) is permitted during this study. Inhaled corticosteroids and bronchodilators to control asthma are permitted.

The introduction of medications or therapies for other medical conditions known to affect AD (for example, high-potency TCS, topical/oral JAK inhibitors, topical/oral phosphodiesterase 4 inhibitor, systemic corticosteroids, MMF, IFN- $\gamma$ , cyclosporine, azathioprine, MTX, phototherapy, biologics or photochemotherapy) are not permitted during the study.

The use of systemic corticosteroids for the treatment of AD is prohibited and requires permanent discontinuation of IP. If used for treatment of an AE (for example, worsening of an existing condition such as asthma exacerbation), the corticosteroid will still be treated as rescue medication per Section [6.5.3](#).

Acute infections can be treated with systemic antibiotics, use of which must be recorded in the eCRF. However, chronic treatment with systemic antibiotics is not permitted.

The use of a tanning booth/parlor is not permitted during the study.

Cannabinoid treatments for AD are prohibited. Planned or anticipated major medical procedures or surgeries should be avoided during the study. See Section [6.5.3](#) for details on approved rescue medications and timing of use.

Prior to therapeutic intervention, an investigator must review the study participant's vaccination record to evaluate the risk of under-immunization to the adolescent study participant.

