**Sex**

7. Male or non-pregnant, non-breastfeeding female.

Contraceptive use by men or women should be consistent with local regulations regarding the methods of contraception for those participating in clinical studies.

- a. For women of childbearing potential (WOCBP): agree to remain abstinent (refrain from heterosexual intercourse) or use a highly effective contraceptive method during the treatment period and for at least 18 weeks after the last dose of lebrikizumab.

NOTE: A WOCBP is defined in Appendix 4, Section [10.4](#).

NOTE: The following are highly effective contraceptive methods: combined (estrogen and progestogen containing) hormonal contraception (oral, intravaginal, transdermal) associated with inhibition of ovulation; progestogen-only hormonal contraception (oral, injectable, implantable) associated with inhibition of ovulation; intrauterine device; intrauterine hormone-releasing system; bilateral tubal occlusion; bilateral tubal ligation; partner who has undergone vasectomy; or sexual abstinence. The reliability of sexual abstinence should be evaluated in relation to the duration of the clinical study and the preferred and usual lifestyle of the patient. Periodic abstinence (for example, calendar, ovulation, symptothermal, or postovulation methods) and withdrawal are not acceptable methods of contraception.

If the highly effective contraceptive methods are contraindicated or strictly declined by patient, acceptable birth control methods may be considered.

These may include combination of both of the following methods:

- male or female condom with spermicide, or
- cap, diaphragm, or sponge with spermicide.

- b. Male patients are not required to use contraception.

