**Prior/Concomitant Therapy**

23. Have received a dose of lebrikizumab in any prior lebrikizumab clinical study.
24. Have had an important side effect from TCS (for example, intolerance to treatment, hypersensitivity reactions, significant skin atrophy, and systemic effects), as assessed by the investigator or treating physician, that would prevent further use.
25. Had treatment with high-potency topical corticosteroids, JAK inhibitors (topical) or phosphodiesterase 4 inhibitor within 7 days prior to the baseline visit (Visit 2).
26. Had treatment with any of the following agents within 4 weeks prior to the baseline visit:
  - a. immunosuppressive/immunomodulating drugs (for example, systemic corticosteroids, cyclosporine, MMF, interferon  $\gamma$  (IFN- $\gamma$ ), JAK inhibitors, azathioprine, MTX, or
  - b. Phototherapy and photochemotherapy for AD.
27. Had treatment with the following prior to the baseline visit:
  - a. an investigational intervention within 8 weeks or within 5 half-lives (if known), whichever is longer
  - b. dupilumab within 8 weeks
  - c. B-cell-depleting biologics, including rituximab, within 6 months, or
  - d. other biologics within 5 half-lives (if known) or 16 weeks, whichever is longer.
28. Have regular use (more than 2 visits per week) of a tanning booth/parlor within 4 weeks of the screening visit.
29. Have been exposed to a live vaccine within 12 weeks prior to the baseline visit or are expected to need/receive a live vaccine during the study or up to 125 days after the last dose of IP.

NOTE: Booster vaccination for measles, mumps, and rubella or varicella-zoster virus may be considered if it is essential based on local guidelines and/or in the opinion of the investigator.

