### **Induction Period**

The use of high-potency topical or systemic treatments for AD is prohibited from baseline through Week 16. Participants who experience intolerable AD symptoms and require treatment should preferably be started on high-potency TCS treatments prior to instituting systemic treatments for AD symptoms, in accordance with best practice.

If systemic treatments (for example, oral corticosteroids, phototherapy, cyclosporine) are required by Week 16, study intervention must be discontinued. The participant should continue to attend all study visits through Week 16 and be assessed for safety and efficacy according to the SoA (Section 1.3). Participants requiring high-potency TCS or systemic rescue medication who complete the study through Week 16 will be eligible to continue to the Escape Arm after the Week 16 visit has been completed. Participants who required systemic treatment must wait for the washout ( $\geq 5$  half-lives of the treatment) prior to entering the Escape Arm.

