### **Maintenance Period**

Intermittent use of high-potency TCS treatments for AD is permitted during the Maintenance Period but must be communicated to the investigator and documented as concomitant medications. Participants who may require short-term systemic treatment for symptoms of AD during the Maintenance Period will be assessed on a case-by-case basis and must be discussed with the Medical Monitor prior to initiating treatment. Participants requiring long-term systemic treatment for symptoms of AD in the Maintenance Period must be discontinued from the study.

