##### **Safety considerations**

- The participant develops any of the following conditions during the study:
  - malignancy (except for successfully treated basal or squamous cell skin carcinoma)
  - HIV/acquired immune deficiency syndrome (AIDS)

- active TB infection or untreated LTBI (Section 8.2.6)
- HCV RNA positive (Section 5.2 and exclusion criterion [19]), or
- HBV DNA positive and clinical assessment consistent with HBV reactivation

NOTE: The HBV DNA result is to be confirmed if initial positive test result is below the level of quantification (Section 8.2.7). The participant is to be referred to, evaluated, and managed by a specialist physician with expertise in evaluation and management of viral hepatitis prior to discontinuation of any immunomodulatory and/or immunosuppressive therapy, including study intervention. Timing of discontinuation from study intervention relative to the initiation of any antiviral treatment for hepatitis is to be based on the recommendation of the consulting specialist physician, in conjunction with the investigator, and aligned with medical guidelines and standard of care.

- The participant answered “yes” to Question 4 or Question 5 on the Suicidal Ideation portion of the C-SSRS or answered “yes” to any of the suicide-related behaviors on the Suicidal Behavior portion of the C-SSRS.

NOTE: A psychiatrist or appropriately trained professional may assist in the decision to discontinue the participant.

- The investigator, after consultation with the sponsor’s designated Medical Monitor, determines that a systemic hypersensitivity reaction has occurred and is related to study intervention administration.
- The participant has any of the following results:
  - total WBC count  $<2000$  cells/ $\mu$ L ( $<2.00 \times 10^3/\mu\text{L}$  or  $2.00 \text{ GI/L}$ )
  - absolute lymphocyte count (ALC)  $<500$  cells/ $\mu$ L ( $<0.5 \times 10^3/\mu\text{L}$  or  $<0.5 \text{ GI/L}$ ), or
  - platelet count  $<50,000$  cells/ $\mu$ L ( $<50 \times 10^3/\mu\text{L}$  or  $<50 \text{ GI/L}$ ).
- Investigator-confirmed diagnosis of PCP during the study.
- The participant has an AE or an SAE or a clinically significant change in a laboratory value that, in the opinion of the investigator, merits discontinuation of study intervention and appropriate measures being taken.

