### 8.2.7. Hepatitis B Testing and Monitoring

Participants who are HBsAg negative and positive for HBcAb and/or HBsAb will automatically have an HBV DNA test performed at screening. Participants who are HBsAg negative, HBcAb negative, and HBsAb positive with a documented history of hepatitis B vaccination will not be required to undergo HBV DNA monitoring at screening. If screening HBV DNA is negative, defined as undetectable HBV DNA, the participant is not excluded, and HBV DNA monitoring is required per the schedule.

If the result of the HBV DNA testing becomes positive at any time during the study, the participant will be permanently discontinued from IP (see Section 7.1.1) and should receive appropriate follow-up medical care, including consideration for antiviral therapy. A specialist physician in the care of participants with hepatitis (for example, infectious disease physician or hepatologist) should be consulted. The timing of discontinuation from IP and any other immunosuppressant therapy should be based on the recommendations of the consulting specialist physician in conjunction with the investigator and medical guidelines/standard of care.

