### **8.4. Treatment of Overdose**

There are no data available on overdoses with lebrikizumab. No dose-related serious adverse drug reactions were observed in healthy volunteers who received single intravenous (IV) doses of up to 5 mg/kg, in patients with mild asthma who received multiple IV doses of up to 3 mg/kg or in participants with asthma or AD who received multiple SC doses of up to 500 mg.

In case of suspected overdose, hematology, chemistry, vital signs, and oxygen saturation should be monitored and supportive care provided as necessary. There is no known antidote for lebrikizumab.

In the event of an overdose, the investigator should:

1. Contact the medical monitor immediately.

2. Closely monitor the participant for any AE/SAE and laboratory abnormalities until lebrikizumab can no longer be detected systemically (at least 18 days).

Decisions regarding dose interruptions or modifications will be made by the investigator in consultation with the medical monitor based on the clinical evaluation of the participant.

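### Two protocol stopping rules conflict with other current text: systemic corticosteroids for atopic dermatitis, and a positive HBV DNA test

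*Protocol*

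**What the plan says.** **Systemic corticosteroids for atopic dermatitis (AD)**

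- Protocol 6.5.1: such use "is prohibited and requires permanent discontinuation of IP". The sentence is not limited to any study period.
- Protocol 6.5.3, Induction Period: oral corticosteroids are one of the named examples of systemic treatment. Study intervention stops, the participant keeps attending visits through Week 16, and those "who complete the study through Week 16 will be eligible to continue to the Escape Arm", subject to a washout of at least 5 half-lives. Section 7.1 repeats the Escape Arm eligibility and the washout. Sections 4.1, 6.1 and 6.3 and SAP 1.2 also provide for Escape Arm entry after systemic rescue. Section 4.1 states that the Escape Arm gives lebrikizumab 250 mg Q2W.
- Protocol 6.5.3, Maintenance Period: "Participants who may require short-term systemic treatment for symptoms of AD during the Maintenance Period will be assessed on a case-by-case basis". The Escape Arm paragraph says the same. Only long-term systemic treatment forces discontinuation.
- Protocol 7.2: a participant who needs another agent shown to be effective for the indication leaves the study before that agent is started.

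**Positive HBV DNA test**

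- Protocol 8.2.7: "If the result of the HBV DNA testing becomes positive at any time during the study, the participant will be permanently discontinued from IP", with a reference to Section 7.1.1.
- Protocol 7.1.1: the listed condition is "HBV DNA positive and clinical assessment consistent with HBV reactivation". A note asks for confirmation when the first positive is below the level of quantification, and refers to Section 8.2.7.

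**Overdose follow-up (query only)**

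- Protocol 8.4: the participant is monitored "until lebrikizumab can no longer be detected systemically (at least 18 days".
- Other post-dose periods: contraception "for at least 18 weeks after the last dose of lebrikizumab" (5.1), and no live vaccine "up to 125 days after the last dose of IP" (5.2, criterion 29). Pregnancy reporting also runs to 125 days (8.3.5).

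**The concern.** A site that works from 6.5.1 and a site that works from 6.5.3 would handle the same participant differently after a course of oral corticosteroids for AD in Induction. One ends study drug for good; the other stops it, keeps the participant on visits and may give lebrikizumab again from Week 16. The HBV rules likewise give two triggers for a permanent stop, in two sections that cite each other.

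At stake are consistent safety handling across sites, how much lebrikizumab these participants receive, and who is counted in the Maintenance W16 Escape Population.

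**Working it through.** This is mainly a comparison of text. The plan states no figure to reproduce.

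**Step 1. One corticosteroid case under each section.** Take a participant given oral corticosteroids for AD before Week 16.

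| Section | Study drug | Visits | Lebrikizumab later? |
|---|---|---|---|
| 6.5.1, with the general rule in 7.1 and 7.1.1 | Stopped permanently | Early termination, then post-treatment follow-up | No |
| 6.5.3 (Induction), 7.1, 4.1, SAP 1.2 | Stopped | Scheduled visits through Week 16 (6.5.3) | Yes, in the Escape Arm after washout |
| 7.2 | Stopped | Leaves the study before the new agent starts | No |

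The first two rows cannot both hold: a stop followed by lebrikizumab in the Escape Arm is not permanent. The third row adds a further outcome if a systemic corticosteroid counts as an effective agent for AD, which 7.2 does not settle. SAP 4.6.1 speaks of drug interruption for systemic rescue, which fits the second row and not the first.

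In the Maintenance Period and Escape Arm, 6.5.3 does not name corticosteroids. A site could apply 6.5.1 to corticosteroids and individual assessment to other agents. That part is ambiguous, not contradictory.

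**Step 2. HBV DNA cases under each section.**

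| Result | 8.2.7 | 7.1.1 |
|---|---|---|
| Positive, quantifiable, clinical picture of reactivation | Permanent stop | Listed condition met |
| Positive, quantifiable, no such picture | Permanent stop | Listed condition not met |
| Positive, below quantification | Permanent stop as written | Confirm first |

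The sections agree in the first row and diverge in the other two. The confirmation note in 7.1.1 points to 8.2.7, which contains no such step.

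**Step 3. Effect on the analyses.**

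- Primary estimand (SAP 4.1.6.1.1): after rescue, values are set to baseline through Week 16.
- Non-responder imputation (SAP 4.1.6.1.3): non-response after rescue.
- MMRM (SAP 4.1.6.1.4): values after rescue are made missing.

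None of these uses an observed post-rescue Week 16 value, so it matters little to them whether the visit took place. A small residue remains under 7.2. If the participant leaves before the agent is given, there is no rescue record, and the handling depends on whether lack of efficacy is recorded as the reason.

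- Maintenance W16 Escape Population (SAP 3): rescue users who move to the Escape Arm belong to it, so its membership depends on the rule followed. SAP 4.1.2.2 gives it no inferential statistics.
- Exposure: a placebo participant treated with systemic corticosteroids in Induction receives lebrikizumab, and so joins the All Lebrikizumab Safety Population, only if the Escape Arm route is followed.

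**Step 4. The overdose figure.** 18 weeks × 7 = 126 days, in line with the 125-day periods. 126 / 18 = 7, so the 18-day minimum is one-seventh of the contraception period. It is also shorter than one Q4W dosing interval (28 days). The documents give no half-life. Purely as an assumption, if each period were meant to cover 5 half-lives, 18 days would imply 18 / 5 = 3.6 days and 125 days would imply 125 / 5 = 25 days. A slip between days and weeks is possible but cannot be shown from these documents.

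**The case against.** **Corticosteroids.** Section 6.5.1 has one outlying sentence against a consistent set elsewhere, and it refers the reader to 6.5.3 for rescue details. It covers only systemic corticosteroids used for AD, so cyclosporine and phototherapy do not fall under its permanent stop. Section 7.1 also makes its own provision for systemic-rescue participants before the general early-termination rule, which weakens any separate claim of conflict over visits. All of this stands and narrows the point. It does not remove it: 6.5.3 and 7.1 name oral corticosteroids and give a different outcome from the sentence that singles them out.

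**HBV.** The list in 7.1.1 is introduced as possible reasons and is not exhaustive, so it does not say that a DNA-positive participant without reactivation continues. Both sections require a specialist and leave timing to that specialist with the investigator. A reader might infer that every DNA-positive participant is affected; only the last two rows of the HBV table are. But the shared timing clause governs when to stop, not whether, and the missing confirmation step remains.

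**Overdose.** A reader might infer a third contradiction. The documents do not support it. Section 8.4 is the only overdose follow-up rule, its operative test is that drug is no longer detected, 18 days is only a floor, and the longer periods serve contraception, vaccination and pregnancy reporting. The figure still deserves a query: PK results are not given to sites (Appendix 2, note g), so a site cannot readily confirm that drug is undetectable and may fall back on the printed number.

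**Impact.** A reader might also infer that the conflict threatens the primary result by losing Week 16 data. The SAP's handling of post-rescue values does not support that.

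**Conclusion.** The point holds for two rules. The corticosteroid conflict is direct in the Induction Period; the Maintenance, Escape Arm and withdrawal wording adds ambiguity. The HBV conflict is confined to participants who are DNA-positive without clinical reactivation, or whose positive result is below quantification.

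The size cannot be put as a number, because the documents do not project how many participants will have either event. In kind, the effect is on participant handling, lebrikizumab exposure and a descriptive population. Inference on the co-primary and major secondary endpoints is largely untouched, provided systemic rescue is recorded as rescue therapy as SAP 6.6.1 requires. The correction is worth making for participant safety and consistent conduct. The overdose minimum is a query about one figure, and nothing here establishes that it is wrong.

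**What to change.** - Reconcile 6.5.1 with 6.5.3 (Induction, Maintenance and Escape Arm paragraphs), 7.1 and 7.2, so that one rule stands for systemic corticosteroids in each period.
- Reconcile 8.2.7 with 7.1.1, so that the trigger and any confirmation step read the same in both and the cross-references lead to the text they promise.
- Align the related wording in 4.1, 6.1 and 6.3, and in SAP 1.2 and 4.6.1, with the rule adopted.
- Ask the sponsor to confirm the 18-day minimum in 8.4 against its source.

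The sponsor's medical team must choose each rule; this review does not say which is right. The cost is a protocol amendment or clarification letter and a notice to sites, plus SAP wording if the adopted rule calls for it. No additional data are needed.

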### **6.5.2. Moisturizers**

A stable dose of non-medicated moisturizers should be used for  $\geq 7$  days prior to the baseline visit (Visit 2) and daily during the study. If daily applications are missed, it will not be considered a protocol violation.

### **6.5.3. Rescue Treatment for Atopic Dermatitis**

The goal of this Phase 3 study is to demonstrate the efficacy and safety of lebrikizumab when used in combination with TCS for AD. However, add-on rescue therapies may be needed if the participant experiences clinical worsening of symptoms that are intolerable.

All rescue treatment usage must be recorded in the eCRF.

### **Induction Period**

The use of high-potency topical or systemic treatments for AD is prohibited from baseline through Week 16. Participants who experience intolerable AD symptoms and require treatment should preferably be started on high-potency TCS treatments prior to instituting systemic treatments for AD symptoms, in accordance with best practice.

If systemic treatments (for example, oral corticosteroids, phototherapy, cyclosporine) are required by Week 16, study intervention must be discontinued. The participant should continue to attend all study visits through Week 16 and be assessed for safety and efficacy according to the SoA (Section 1.3). Participants requiring high-potency TCS or systemic rescue medication who complete the study through Week 16 will be eligible to continue to the Escape Arm after the Week 16 visit has been completed. Participants who required systemic treatment must wait for the washout ( $\geq 5$  half-lives of the treatment) prior to entering the Escape Arm.

